**Evaluating the Safety and Effectiveness of the Omnipod® 5
Automated Insulin Delivery System in Patients with Type 2
Diabetes**

IDE G190270

Version 5.0

27 July 2021

Insulet Corporation

[name]

[name]

Confidentiality Statement:

The information in this document contains trade secrets and commercial information that are privileged or confidential and may not be disclosed unless such disclosure is required by applicable law or regulations. In any event, persons to whom the information is disclosed must be informed that the information is privileged or confidential and may not be further disclosed by them. These restrictions on the disclosure shall apply equally to all future information supplied to you, which is indicated as privileged or confidential.

PROTOCOL SUMMARY

Protocol title	Evaluating the safety and effectiveness of the Omnipod 5 Automated Insulin Delivery System in patients with type 2 diabetes
Protocol ID	G190270
Purpose	To obtain feasibility data using the Omnipod 5 Automated Insulin Delivery System in patients with type 2 diabetes with suboptimal glycemic control.
Design	This study is a multi-center, feasibility study
Enrollment	
A total of up to 36 subjects will be enrolled in the study to obtain a minimum of 24 evaluable subjects enrolled across 3-6 clinical study sites.
 
The study subjects will be separated into 2 groups (N=12 each), depending on their previous insulin therapy with approximately 50% of subjects from each group, CGM naive:
 
Basal-Bolus – Group A
 
 • 2 weeks standard therapy – using multiple daily injections (MDI) and Dexcom G6 CGM, followed by: • 4 weeks OP5 in Automated Mode with optional bolus, followed by: • 4 weeks OP5 in Automated Mode with simplified bolus • 6 month extension using Automated Mode (optional) 
Basal – Group B
 
 • 2 weeks standard therapy – using basal injection only and Dexcom G6 CGM, followed by: • 2 weeks OP5 in Manual Mode with Dexcom G6 CGM – with fixed basal rate, no bolus, followed by: • 4 weeks OP5 in Automated Mode with optional bolus, followed by: 
 ◦ If % time in range 70-180 mg/dL during Automated Mode is ≤50%, 4 weeks OP5 in Automated Mode with simplified bolus, OR ◦ If % time in range 70-180 mg/dL during Automated Mode is >50%, 4 weeks OP5 in Automated Mode with optional bolus • 6 month extension using Automated Mode(optional)
Indication	
The Omnipod 5 (OP5) is a single hormone insulin delivery system intended for the management of diabetes in persons requiring insulin. Continuous subcutaneous insulin infusion may be delivered by user-defined settings (manual mode) or automatically adjusted in response to feedback from a continuous glucose monitor (CGM).
 
The Omnipod 5 can automatically increase insulin delivery based on CGM sensor glucose values and can decrease or suspend delivery of insulin when the glucose value falls below or is predicted to fall below predefined threshold values. The Omnipod 5 is interoperable with compatible iCGMs and ACE pumps.
 
The Omnipod 5 is designed to assist patients with diabetes in achieving glycemic targets set by their health care providers.

Study duration	The study is expected to be completed within 18-months which includes clinical site initiation to completion and all data entry and monitoring procedures. The results from the 6 month extension for both groups will be evaluated and submitted separately from the other phases of the study.
Investigational devices	
The Omnipod 5 is comprised of the following components:
 
 • Omnipod 5 tubeless, insulin delivery alternate controller enabled (ACE) pump (Pod) powered by the Horizon algorithm • Omnipod 5 Personal Diabetes Manager (PDM) which is a Samsung J3 locked down Android device that operates the Horizon App. • Dexcom G6 - Continuous Glucose Monitoring (CGM) system
Non-investigational, commercially available devices	
 • Contour® Next One blood glucose meter (Ascensia Diabetes Care, [name])
Primary safety objective	To evaluate the safety of the Omnipod 5 Automated Insulin Delivery System in patients with type 2 diabetes.
Primary safety endpoints	
The primary safety objective will be evaluated by summarizing the following during Automated Mode:
 
 • Hyperglycemia - Overall percentage of time ≥ 250 mg/dL during all phases of Automated Mode • Hypoglycemia – Overall percentage of time < 54 mg/dL during all phases of Automated Mode 
The results from the 6 month extension for both groups will be evaluated and submitted separately from the other phases of the study.

Secondary objective	To evaluate additional glycemic measures of effectiveness of the Omnipod 5 Automated Insulin Delivery System.
Secondary endpoints	
Per subject glucose metrics during Automated Mode use will be compared to the standard therapy phase overall, separately for Group A and Group B:
 
 • Mean glucose • % of time in range 70-180 mg/dL • % of time > 180 mg/dL • % of time ≥ 250 mg/dL • % of time ≥ 300 mg/dL • % of time < 70 mg/dL • % of time < 54 mg/dL • Standard deviation • Coefficient of variation • Total daily insulin (TDI) (units, units/kg) • End of study A1C vs. baseline A1C 
The results from the 6 month extension for both groups will be evaluated and submitted separately from the other phases of the study.

Patient Reported Outcomes	Various subject completed questionnaires will be used to evaluate general and disease-specific quality of life, and device usability.
Eligibility criteria	
Inclusion Criteria
 
Subjects must meet all the following criteria to be included in the study:

	
 1. Age at time of consent 18-75 years 2. Diagnosed with type 2 diabetes on insulin therapy by injection: basal-bolus (12 subjects) or basal only (12 subjects) regimens 3. A1C 8.0-12.0% 4. Has not used an insulin pump within 3 months of screening 5. Willing to use only the following types of insulin during the study: Humalog, Novolog, Admelog or Apidra during the study 6. Maximum insulin dose of 200 units/day 7. Stable doses over the last 4 weeks of other glucose-lowering medications as determined by Investigator 8. Willing to wear the system continuously throughout the study 9. Deemed appropriate for pump therapy per investigator's assessment considering previous history of severe hypoglycemic and hyperglycemic events, and other comorbidities 10. Investigator has confidence that the subject has the cognitive ability and can successfully operate all study devices and can adhere to the protocol 11. Must be willing to use the Dexcom App on the Omnipod 5 PDM as the sole source of Dexcom data (except for the Dexcom Follow App) during Automated Mode 12. Subjects scoring ≥ 4 on the Clarke Questionnaire must agree to have an overnight companion, defined as someone who resides in the same home or building as the study subject and who can be available overnight 13. Able to read and speak English fluently 14. Willing and able to sign the Informed Consent Form (ICF)
	
Exclusion Criteria
 
Subjects who meet any of the following criteria will be excluded from the study:
 
 1. A medical condition, which in the opinion of the investigator, would put the subject at an unacceptable safety risk 2. Planned major surgery during the study 3. History of severe hypoglycemia in the past 6 months 4. History of diabetic ketoacidosis (DKA) in the past 6 months, unrelated to an intercurrent illness, infusion set failure or initial diagnosis 5. Diagnosed with a blood dyscrasia or bleeding disorder 6. Plans to receive blood transfusion over the course of the study 7. Currently diagnosed with anorexia nervosa or bulimia 8. Currently on hemodialysis 9. History of adrenal insufficiency 10. Has taken oral or injectable steroids within the past 8-weeks or plans to take oral or injectable steroids during the study 11. Unable to tolerate adhesive tape or has any unresolved skin condition in sensor or pump placement 12. Plans to use insulin other than U-100 insulin during the Omnipod 5 phase of the study 13. Cardiac disease with functional status New York Heart Association Class III or IV or current or known history of coronary artery disease that is not stable with medical management, including unstable angina, or angina that prevents moderate exercise despite medical management, or a history of myocardial infarction, percutaneous coronary intervention, or coronary artery bypass grafting within the previous 12-months. 14. Pregnant or lactating, or is a woman of childbearing potential and not on acceptable form of birth control (acceptable includes abstinence, condoms, oral/injectable contraceptives, IUD, or implant)

	
15. Participation in another clinical study using an investigational drug or device other than the Omnipod 5 in the preceding 30-days or intends to participate during the study period
 
16. Unable to follow clinical protocol for the duration of the study or is otherwise deemed unacceptable to participate in the study per the investigator's clinical judgment

Study schedule	
The study subjects will be separated into 2 groups, depending on their previous insulin therapy with approximately 50% of subjects from each group, CGM naive:
 
Basal-Bolus – Group A (N=12)
 
 • 2 weeks standard therapy – using multiple daily injections (MDI) and Dexcom G6 CGM, followed by: • 4 weeks OP5 in Automated Mode with optional bolus, followed by: • 4 weeks OP5 in Automated Mode with simplified bolus • 6 month extension using Automated Mode (optional) 
Basal – Group B (N=12)
 
 • 2 weeks standard therapy – using basal injection only and Dexcom G6 CGM, followed by: • 2 weeks OP5 in Manual Mode with Dexcom G6 CGM – with fixed basal rate, no bolus, followed by: • 4 weeks OP5 in Automated Mode with optional bolus, followed by: 
 ◦ If % time in range 70-180 mg/dL during Automated Mode is $\leq 50\%$, 4 weeks OP5 in Automated Mode with simplified bolus, OR ◦ If % time in range 70-180 mg/dL during Automated Mode is $> 50\%$, 4 weeks OP5 in Automated Mode with optional bolus • 6 month extension using Automated Mode (optional) 
Following the subject screening, enrollment, and device training, subjects from both groups will commence the outpatient 2-week standard therapy phase using a Dexcom G6 CGM. After completion of the standard therapy phase, subjects will be trained on the use of Omnipod 5 and transition to either Automated Mode or Manual Mode use depending on which group they have been assigned.
 
Current Dexcom G6 CGM users may provide data from a 14-day period within the last 30-days. For non-G6 users, subjects will wear a study CGM, in blinded mode, to record glucose measurements over 14-days while subjects manage their diabetes at home per their usual routine and remaining on their current MDI, and sensor, if applicable, for 14-days.
 
Subjects in Group A will use Automated Mode for 4 weeks with optional boluses followed by 4 weeks of simplified boluses. Subjects will then be eligible to transition to the optional 6 month extension phase.
 
Subjects in Group B will use the system for 2 weeks in Manual Mode with a CGM and a fixed basal rate and no bolus. After completion of Manual Mode, Group B subjects will commence using the system in Automated Mode for 4 weeks with optional boluses. After completion of 4 weeks of Automated Mode, subjects will continue using Automated Mode for 4 weeks but will either continue using a simplified bolus or optional bolus depending on their time in range of 70-180 mg/dL over the previous 4 weeks of Automated Mode use.


	Subjects will then be eligible to transition to the optional 6 month extension phase.
Safety	An independent Medical Monitor will be responsible for individual and timely review of adverse events. The Medical Monitor will be a physician with relevant therapeutic and medical expertise that is not participating as an Investigator in the study and does not have a financial, scientific, or other conflict of interest with the clinical study.
Statistical Analysis	
General Statistical Methods
 
Standard statistical methods will be employed to analyze all data. Data collected in this study will be presented using summary tables and subject data listings. Unless otherwise noted, all p-values will be considered significant at a two-sided significance level of 5%. Continuous variables will be summarized using descriptive statistics, including count, mean, median, standard deviation (SD), minimum and maximum, and first and third quartiles. If the observed data are found not to follow a normal distribution, appropriate non-parametric methods may be employed. Categorical variables will be summarized by frequencies and percentages. Unless explicitly stated otherwise, percentages will utilize a denominator corresponding to the number of unique subjects.
 
Sample Size
 
This is a non-powered, multi-center, feasibility study. The sample size for the study is not hypothesis-driven and has been chosen to gather adequate safety and clinical performance data of the algorithm in the type 2 population.
 
Primary Endpoint
 
There are no hypotheses associated with the primary safety endpoints. The per subject percentage of time in each of the ranges will be summarized separately for each group no between-group analyses are planned. Standard summary statistics (i.e., mean, standard deviation, median, range) will be provided. Any statistical comparisons will be conducted at a two-sided significance level of 5%. Data from all sites will be pooled for all analyses and summaries; no separate analyses by site or formal testing of poolability will be performed.
 
Secondary Endpoint
 
There are no hypotheses associated with the secondary endpoints. Each endpoint will be summarized separately for each group; no between-group analyses are planned. Standard summary statistics (i.e., mean, standard deviation, median, range) will be provided. Any statistical comparisons will be conducted at a two-sided significance level of 5%.
 
Safety
 
All adverse events reported over the course of the study will be summarized and tabulated by group, study phase if applicable, event category, seriousness, severity, and relationship to the study procedure and the investigational device. For the purposes of summarization, an event will be considered “Related” if the relationship was deemed as “Possibly Related” or “Related”. In cases where the same event is reported more than once per subject, the event will only be counted once in the incidence table(s).

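### Do primary CGM endpoints taken over the whole of Automated Mode hide what happens in each 4-week bolus phase?

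*Combined protocol and SAP*

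**What the plan says.** All references are to the Protocol Summary.

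- **Primary safety objective:** "To evaluate the safety of the Omnipod 5 Automated Insulin Delivery System in patients with type 2 diabetes".
- **Primary safety endpoints:** hypoglycemia is "Overall percentage of time < 54 mg/dL during all phases of Automated Mode"; hyperglycemia uses the same construction at 250 mg/dL and above. The text directly beneath adds: "The results from the 6 month extension for both groups will be evaluated and submitted separately from the other phases of the study".
- **Secondary endpoints:** the planned comparison reads "Per subject glucose metrics during Automated Mode use will be compared to the standard therapy phase overall, separately for Group A and Group B". The list also holds "End of study A1C vs. baseline A1C", which has one end-of-study value and cannot be split by phase.
- **Study schedule, Group A:** "Subjects in Group A will use Automated Mode for 4 weeks with optional boluses followed by 4 weeks of simplified boluses".
- **Enrollment and Study schedule, Group B:** after a first 4 weeks with optional bolus, "If % time in range 70-180 mg/dL during Automated Mode is ≤50%, 4 weeks OP5 in Automated Mode with simplified bolus"; above that cut the subject stays on optional bolus. The narrative says that these subjects "will either continue using a simplified bolus or optional bolus depending on their time in range".
- **Statistical Analysis:** the study is not powered and no hypotheses are attached to the primary or secondary endpoints. Per-subject percentages are summarized within each group by mean, SD, median and range. General Statistical Methods adds quartiles and subject listings. Only the Safety paragraph, on adverse events, names study phase as a tabulation factor.

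**The concern.** The design deliberately changes how boluses are given halfway through Automated Mode, yet the planned CGM tables average across that change. If time below 54 mg/dL or at or above 250 mg/dL were concentrated in one 4-week period, the group mean would show it at reduced size. In Group B the reduction would be greater, because only some subjects move to simplified bolus. A feasibility study is a natural place to look for such a pattern, and adverse events may be broken down by phase while CGM metrics are not. The extension also runs in Automated Mode, so a reader might further wonder whether it is included in all phases. At stake would be a safety signal tied to one bolus regimen that the summary tables understate.

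**Working it through.** **Inputs.** From the documents: 12 subjects per group; 4 + 4 = 8 weeks of Automated Mode before the extension in each group; a time-in-range cut of 50% in Group B. The documents give no expected CGM values, SDs or path proportions, so every such figure below is an assumption. There is no planned figure to reproduce.

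**1. How much is diluted.** If second-phase CGM coverage is r times that of the first, the second phase has weight r/(1 + r) in the overall percentage.

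- r = 1: 1/2 = 0.500
- r = 0.7 (assumed): 0.7/1.7 = 0.412

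An excess D in the second phase therefore appears in the Group A mean as 0.41D to 0.50D. In Group B, with fraction f on simplified bolus and equal coverage, it appears as f × D/2:

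- 3 of 12: 0.25/2 = 0.125D
- 6 of 12: 0.50/2 = 0.25D
- 9 of 12: 0.75/2 = 0.375D

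Example with assumed values: time below 54 mg/dL of 0.2%, rising to 1.0% under simplified bolus. Group A overall is (0.2 + 1.0)/2 = 0.6%. Group B overall is 0.2 + f × 0.8/2, that is 0.3%, 0.4% or 0.5% for 3, 6 or 9 subjects.

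**2. Whether dilution is an error.** These overall values are correct answers to the question posed: how much time do subjects spend in the range while using the system in Automated Mode? The objective concerns the system, not one bolus regimen against another. No test, threshold or decision rule depends on a phase-specific value, so the averaging cannot turn a failure into a success.

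**3. What remains visible.** Dilution by f applies to the group mean. If one subject of 12 has an excess D in one phase, the group mean moves by D/(2 × 12) = D/24, but that subject's own value moves by D/2. The planned range reports the maximum, and subject listings are planned.

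**4. What a split could show.** In Group A, optional bolus always comes first, so regimen cannot be separated from time on the system. In Group B, the path is chosen on first-phase time in range, which brings two problems.

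*Small paths.* With X ~ Binomial(12, p), where p is the assumed share at or below 50%, the probability that the smaller path has 2 or fewer subjects is:

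| p | Probability |
|---|---|
| 0.50 | 4% |
| 0.25 or 0.75 | 39% |
| 0.10 or 0.90 | 89% |

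*Regression to the mean.* Let b and w be the between- and within-subject SDs of time in range (assumed), with s = √(b² + w²) and half the subjects on each path. With no regimen effect, the expected first-to-second-phase change on the lower path is (w²/s) × φ(0)/0.5, where φ(0)/0.5 = 0.798.

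- b = 18, w = 5: 25/18.68 × 0.798 = +1.07 points
- b = 15, w = 7: 49/16.55 × 0.798 = +2.36 points
- b = 12, w = 9: 81/15 × 0.798 = +4.31 points

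The upper path shows the same change with the opposite sign.

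The change from standard therapy to the first phase is also distorted, and not by a mirror-image amount. If true levels on the two treatments correlate at 0.8 with equal spread (b = 15, w = 7), a simulation gives −4.51 on the lower path, beside +2.37 from first to second phase. The two match in size only at correlation 1 with equal spread. None of these time-in-range figures carries over to the two primary endpoints.

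**5. The extension.** The statement that it is evaluated and submitted separately stands directly under the two primary endpoints and again under Secondary endpoints. The main analysis therefore covers the 8 weeks only.

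**The case for a change.** The strongest case for the concern is that the study exists to gather feasibility data, the regimen change is deliberate, and nothing in the available text plans a by-phase or by-path summary of CGM or insulin metrics. The dilution is plain arithmetic. Adverse-event tables by phase do not report time below 54 or at or above 250 mg/dL, and no phase layout is stated for the listings. Extra columns would need no new data and would leave sample size and alpha unchanged.

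All of this is correct, and a descriptive table by 4-week phase with subject counts would be reasonable to produce. It does not make the plan faulty. The excess it would reveal is hypothetical, nothing in the plan prevents such a table, and the available text is a summary, so a fuller analysis section may already contain one. For the secondary metrics, the reading that the two phases are pooled is itself an inference: only the primary endpoints refer to all phases. Within-path columns for Group B would also need warnings about selection and small numbers before they could be read safely.

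**Conclusion.** The concern does not hold. The overall endpoints match the stated objective, are purely descriptive, and give sound results if the plan is followed as written. The reduction to about D/2 in Group A and 0.125D to 0.375D in Group B is real for group means. It rests on assumed CGM coverage (0.41D to 0.50D in Group A at coverage ratios of 0.7 to 1) and on assumed path sizes of 3 to 9 of 12. It changes no planned endpoint, test or conclusion. Phase-level columns could describe the data but could not attribute a difference to bolus regimen. The exclusion of the extension is already stated. What is left is a reporting preference, and it lapses if by-phase tables exist in the full protocol or SAP.

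### Does the plan need a pre-specified glucose summary for Group B's two weeks in Manual Mode?

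*Combined protocol and SAP*

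**What the plan says.** All places cited are in the Protocol Summary.

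- **Study schedule, Group B:** 2 weeks of standard therapy, 2 weeks of Manual Mode, 4 weeks of Automated Mode with optional bolus, then 4 more weeks of Automated Mode with the bolus approach set by each subject's time in range. On the second of these: "Subjects in Group B will use the system for 2 weeks in Manual Mode with a CGM and a fixed basal rate and no bolus". Group A goes straight from standard therapy to Automated Mode.
- **Study schedule, baseline sensor:** "For non-G6 users, subjects will wear a study CGM, in blinded mode, to record glucose measurements over 14-days".
- **Primary safety endpoints:** "The primary safety objective will be evaluated by summarizing the following during Automated Mode". The two measures are time at or above 250 mg/dL and time below 54 mg/dL.
- **Secondary endpoints:** "Per subject glucose metrics during Automated Mode use will be compared to the standard therapy phase overall", by group. The list has nine CGM metrics, total daily insulin, and "End of study A1C vs. baseline A1C".
- **Statistical Analysis, Sample Size:** the study is not powered, and the sample "has been chosen to gather adequate safety and clinical performance data of the algorithm in the type 2 population".
- **Statistical Analysis, General Statistical Methods and Safety:** collected data are to appear in summary tables and subject listings. Adverse events are tabulated by study phase where that applies.

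**The concern.** Group B moves from injections to the pump in Manual Mode, and then to automated delivery. The planned comparison uses only the first and last of these three states. A change from standard therapy to Automated Mode could come wholly from the pump, wholly from the later step, or from both, and no listed endpoint tells these apart. A1C from baseline to end of study spans the Manual Mode weeks but cannot separate them.

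Two statements in the plan make this look more than cosmetic. The sample size rationale refers to the performance of the algorithm, and Manual Mode is the only phase on the same hardware where the algorithm does not adjust delivery. The Indication also covers delivery by user-defined settings, yet the CGM safety measures are not named for that phase. A reader might credit automation with a gain that came earlier, or miss time in low or high glucose during Manual Mode.

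**Working it through.** **1. The plan's own figure.** Two groups of 12 give 12 + 12 = 24, the stated minimum of evaluable subjects. There is no power calculation to reproduce.

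**2. Share of exposure (Study schedule).** Group B device time in the main study, without the optional extension, is 2 + 4 + 4 = 10 weeks. Manual Mode is 2/10 = 20%. In subject-weeks at n = 12 it is 12 × 2 = 24 of 12 × 10 = 120. With the standard therapy weeks the main study lasts 12 weeks, and the share is 2/12 = 16.7%. These are shares of time, not effects on any result.

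**3. Can the change be split?** For one subject and one metric, let S, M and A be the values in standard therapy, Manual Mode and all of Automated Mode. Then

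A − S = (M − S) + (A − M).

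The planned contrast is the left side. From that alone, a 15-point change (illustrative) fits steps of 0 + 15, 5 + 10, 10 + 5 or 15 + 0 equally well. The split needs only one more value per subject, M, and CGM is worn in Manual Mode. So the listed endpoints do not make the split, but the data allow it.

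**4. What the split would show.** What changes at each step, from the Study schedule:

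| Step | What changes |
|---|---|
| Standard therapy to Manual Mode | Injections to pump. For subjects on a blinded sensor at baseline, probably also sight of glucose readings, since the Manual Mode sensor is not described as blinded |
| Manual Mode to Automated Mode | Automated adjustment, and boluses go from none to optional (or simplified, for some subjects, in the last 4 weeks) |

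The order is the same for everyone and there is no concurrent control. Neither step isolates the algorithm.

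**5. Choice of Automated window.** Let A1 and A2 be the two 4-week Automated values. Using A1 alone keeps one bolus condition for all of Group B, but then (M − S) + (A1 − M) = A1 − S. If the planned contrast pools both periods with equal weight, it is (A1 + A2)/2 − S. The two differ by (A2 − A1)/2, so a first-period split need not add up to the planned result.

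**6. Precision.** The 95% half-width of a paired mean difference at n = 12 is t(0.975, 11)/√12 × SD = 2.201/3.464 × SD = 0.635 × SD. The documents give no SD. For assumed SDs in percentage points of time in range:

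| SD of paired differences | Half-width |
|---|---|
| 5 | 3.2 |
| 10 | 6.4 |
| 15 | 9.5 |
| 20 | 12.7 |

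The multiplier also applies to the planned contrast, though the SD may differ. In about 6 CGM-naive subjects it rises to 2.571/2.449 = 1.05.

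**7. Size of a full set of contrasts.** Nine CGM metrics with four contrasts each (Manual minus standard, Automated minus Manual in a main window, and two sensitivity windows) make 9 × 4 = 36 intervals, before total daily insulin.

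**The case for a change.** The best case for a change is that it costs almost nothing. The CGM data are already collected, and one added column would need no extra subjects, visits or procedures. Naming the summary in advance would also stop analysts from choosing a window after seeing results, which matters because the last 4 Automated weeks divide Group B by earlier time in range. The Indication adds a safety argument: delivery by user-defined settings is part of the product, and time below 54 and at or above 250 mg/dL in that mode is of interest in its own right.

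Much of this stands. No Manual Mode glucose table is named in the Protocol Summary, the general sentence on tables and listings specifies no metric or window, and a descriptive column would be useful. But this is an argument for a fuller report. It shows no planned result to be biased, mislabelled or unanswerable. The window risk arises mainly if someone makes the extra contrast, and the plan makes no claim that depends on it. Adverse events in Manual Mode can already appear in the by-phase tabulation.

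**Conclusion.** No change to the plan is needed. The primary and secondary objectives concern the automated system as a whole, and the Automated-versus-standard comparison answers them for Group B without Manual Mode data. Limiting the CGM endpoints to the phases where the algorithm adjusts delivery also fits the sample size rationale. The gap is one unnamed descriptive summary, covering 20% of Group B's main-study device time. Analysts can fill it from collected data under the general commitment to tabulate and list.

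A formal set of step contrasts would gain little: it would not separate automation from the change in bolus policy or from phase order, and each interval would be ±0.635 SD wide. If a Manual Mode column is shown, a note on those two limits is enough.

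This rests on 12 evaluable subjects in Group B, on assumed SDs, and on the text available, which is the Protocol Summary. A fuller statistical section could only narrow the gap. The direction and size of any Manual-minus-standard change are unknown and may be zero. The conclusion would differ if the report claimed an effect of the algorithm separate from the pump, but the plan makes no such claim.

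### Adverse event tables split by phase give once-per-subject incidence with no event count or subject-time, although the phases differ in length (minor)

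*Combined protocol and SAP*

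**What the plan says.** The Safety paragraph under Statistical Analysis (Protocol Summary) sets the scope of the tables: "All adverse events reported over the course of the study will be summarized and tabulated by group, study phase if applicable", followed by event category, seriousness, severity and relationship. It closes with the counting rule: "In cases where the same event is reported more than once per subject, the event will only be counted once in the incidence table(s". General Statistical Methods supplies the denominator: "Unless explicitly stated otherwise, percentages will utilize a denominator corresponding to the number of unique subjects". The same paragraph provides for listings: "Data collected in this study will be presented using summary tables and subject data listings".

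The Study schedule fixes the phase lengths. Both groups start with 2 weeks of standard therapy. For Group A, "Subjects in Group A will use Automated Mode for 4 weeks with optional boluses followed by 4 weeks of simplified boluses". For Group B, "Subjects in Group B will use the system for 2 weeks in Manual Mode", and then for two Automated Mode periods of 4 weeks each. An optional 6-month extension follows for both groups, and its results are evaluated and submitted separately.

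The text does not mention a count of events, time under observation or an event rate for adverse events.

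**The concern.** The proportion of subjects with at least one event rises with the length of observation, even when the underlying event rate does not change. If the tables are split by phase, a reader who sets the 2-week standard therapy column beside an Automated Mode column would tend to see a higher figure on the device from phase length alone. The distortion runs against the device.

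A subject with several episodes also appears in the incidence table exactly as a subject with one. In a feasibility study whose size was chosen to gather safety and performance data, the adverse event tables are the main planned summary of harms other than out-of-range glucose. They should show both how many subjects were affected and how often.

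**Working it through.** The plan states no adverse event rate and no derived figure, so there is nothing to reproduce. What follows illustrates the mechanism.

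**Inputs from the plan.** 12 subjects per group (Enrollment); phases of 2 weeks and 4 weeks, or 8 weeks if the two Automated Mode periods are pooled (Study schedule).

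**Assumptions.** One event type with a constant Poisson rate *r* per subject-week, the same in every phase: 0.05, with a range of 0.01 to 0.10. All 12 subjects complete each phase. The once-per-subject count starts afresh in each phase.

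**Formulas.** For a phase of *w* weeks:
- incidence = 1 − exp(−*rw*)
- expected events = 12*rw*
- expected subjects counted = 12[1 − exp(−*rw*)]
- events not shown = expected events − expected subjects counted

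| *r* | *w* | Incidence | Events | Subjects counted | Not shown |
|---|---|---|---|---|---|
| 0.01 | 2 | 1.98% | 0.24 | 0.24 | 0.00 |
| 0.01 | 4 | 3.92% | 0.48 | 0.47 | 0.01 |
| 0.01 | 8 | 7.69% | 0.96 | 0.92 | 0.04 |
| 0.05 | 2 | 9.52% | 1.20 | 1.14 | 0.06 |
| 0.05 | 4 | 18.13% | 2.40 | 2.18 | 0.22 |
| 0.05 | 8 | 32.97% | 4.80 | 3.96 | 0.84 |
| 0.10 | 2 | 18.13% | 2.40 | 2.18 | 0.22 |
| 0.10 | 4 | 32.97% | 4.80 | 3.96 | 0.84 |
| 0.10 | 8 | 55.07% | 9.60 | 6.61 | 2.99 |

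**Effect of phase length.**
- 4 weeks against 2 weeks: 18.13/9.52 = 1.90 at *r* = 0.05; 3.92/1.98 = 1.98 at 0.01; 32.97/18.13 = 1.82 at 0.10.
- 8 pooled weeks against 2 weeks: 32.97/9.52 = 3.46; 7.69/1.98 = 3.88; 55.07/18.13 = 3.04.

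A second grid of rates, 0.5 to 8 per subject-year (about 0.01 to 0.15 per week), gives ratios of 1.7 to 2.0 and 2.7 to 3.9, so the result does not hinge on the rates chosen.

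**Recurrences.** At *r* = 0.05, about 0.2 of 2.4 events per 4-week period are not shown, or 0.8 of 4.8 if the 8 weeks are pooled. If events cluster in a few subjects, the share not shown is larger than under this model.

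**What the added columns do.** Full completion gives 12 × 2 = 24, 12 × 4 = 48 and 12 × 8 = 96 subject-weeks. At *r* = 0.05 the expected rates are 1.2/24 = 2.4/48 = 4.8/96 = 0.05, the same in each phase.

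**Precision.** Exact Poisson 95% intervals: 5 events in 96 subject-weeks is 0.052 per week (0.017 to 0.122); 1 event in 24 subject-weeks is 0.042 (0.001 to 0.232).

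**The case against.** The strongest reply is that the counting rule is not an error: counting a subject once is what an incidence table does. That stands, and the rule should stay. The gap is only the missing companion count and exposure.

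Second, no between-phase adverse event comparison or hypothesis is stated, the phase split is conditional, and the planned lengths are there for any reader to see. This also stands, and it is why the point is minor. Some contrasts are not affected by length at all: standard therapy and Manual Mode in Group B both last 2 weeks, and the two Automated Mode periods are equal. Still, the plan compares glucose metrics in Automated Mode with standard therapy, so adverse event columns for the same phases invite the same reading.

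Third, recurrences remain in the subject listings, and the Medical Monitor reviews events individually. That is true, but listings are not a summary and supply no denominator.

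Fourth, the promise to summarize all events may already include event counts, the counting rule may be aimed at duplicate reports of one event, or fuller rules may lie outside this summary. All are possible, and the text settles none of them. If event counts are already intended, one sentence confirms it.

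Two stronger readings are tempting. A reader might set the 2-week phase against the 6-month extension, where the gap would be largest. The extension is reported separately, so the plan does not put those columns side by side. A reader might also infer that standard therapy has less adverse event observation among current sensor users, because "Current Dexcom G6 CGM users may provide data from a 14-day period within the last 30-days". That sentence concerns glucose data and says nothing about adverse event collection. Nor does "with approximately 50% of subjects from each group, CGM naive" establish how many subjects are G6 users or would take the option. No shortfall in observation can be derived from it.

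**Conclusion.** The point holds as a minor and inexpensive improvement in presentation. Where the tables are split by phase, incidences from phases of different length should not be read against each other, and the incidence table does not show recurrences.

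The better guide to size is the ratio of about 1.9 for a 4-week period against 2 weeks, because the schedule lists the two Automated Mode periods separately. The ratio of about 3.5 applies only if they are pooled. In either layout, fewer than one event per group goes unshown at the central rate. Every rate here is assumed, and the model takes a constant Poisson rate with full completion.

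The primary safety endpoints are percentages of time in glucose ranges and are untouched. Nothing here supports a claim that the safety analysis is invalid or that recurrences are lost.

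**What to change.** Keep the once-per-subject incidence and add to the Safety paragraph:

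> *Beside each incidence, by group and by each phase tabulated, the total number of events (recurrences included), the subject-weeks under adverse event observation and events per subject-week will be shown descriptively, without a test; the extension will be shown the same way in its separate report.*

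The cost is one sentence and three table columns. It needs event onset dates and each subject's phase start and stop dates. The text does not say these are collected, but tabulating by phase requires them anyway. No visit, treatment or sample size changes. The drawback is that rates from about 12 subjects per group will be imprecise, as the intervals above show, which is why no test should be attached.
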